Demographically and clinically diverse participants are necessary to ensure breast cancer clinical trial results are generalizable at the population level, yet trial participants rarely represent the real-world population in which the intervention will be applied.¹⁻⁵ Breast cancer patients of low socioeconomic status are one population group underrepresented in clinical trials, potentially due to the high out-of-pocket costs associated with trial participation.^{6, 7} Direct research costs uncovered by the trial sponsor, such as the trial treatment itself or trial-related labs, imaging, procedures, or out-of-network care, as well as indirect costs of participation, such as travel or time off work, are at the expense of the patient.⁸⁻¹¹ Thus, it's estimated that almost half of patients in early phase oncologic clinical trials spend at least \$1,000 per month out-of-pocket to participate.¹² The high out-of-pocket costs associated with trial participation drive underrepresentation of economically vulnerable women with breast cancer in clinical trials and could exacerbate existing inequitable clinical outcomes.¹

Our previous nationwide survey found 1 in 4 respondents reported payment or support for trial participation, such as transportation, childcare, or paid time off from work, would influence their decision to participate.¹³ Thus, reimbursement for trial participation costs could aid in reducing the financial toxicity (defined as high out-of-pocket costs and accompanying financial distress¹⁴) experienced by trial participants and allow for more diverse trial samples by dismantling recruitment and retention barriers. Reimbursement for clinical trial participation could be particularly impactful for women with breast cancer enrolled in clinical trials at UAB, since this population includes many patients who are Black (who experience an Alabama poverty rate of 28% vs. 12% for White patients¹⁵) or who travel from rural areas across the state of Alabama to receive care. However, the impact of reimbursement is currently unclear. Thus, the critical first step in testing the impact of reimbursement is identifying appropriate levels of reimbursement needed to compensate for trial-related out-of-pocket costs. Without such information, breast cancer patients of low socioeconomic status could face barriers to trial participation, preventing them from receiving new, cutting-edge treatment and biasing the evidence base for real-world clinical practice guidelines.

2. Preliminary Studies

One in three UAB oncology patients experience financial toxicity. Our study of 1,564 UAB oncology patients found that 29% were experiencing financial distress. Reported distress also differed by race, with 40% of Black patients screened positive for financial distress compared to 23% of White patients. Differences in types of financial difficulties were seen comparing Black and White patients, including 32% vs. 15% reporting difficulty with upfront medical payments and 25% vs. 10% reporting financial difficulties with transportation for care, respectively (*presented at the O'Neal Comprehensive Cancer Center's 22nd Annual Research Retreat*).

Cost-related barriers to care impact clinical trial participation. Our previous study of 3,682 U.S. adult respondents to the Health Information National Trends Survey found that over half (55%) of respondents reported at least one cost-related consideration as very influential to trial participation, including if usual care was not covered by insurance (reported by 42%), payment for participation (24%), or support for participation, such as transportation, childcare, or paid time off from work (24%). Notably, respondents with lower perceived income had double the odds of reporting a cost-related consideration as very influential to trial participation than those with higher perceived income.¹³

Socioeconomic inequities in clinical trial enrollment exist for patients with breast cancer at UAB. In our study of women with breast or ovarian cancer prescribed a therapeutic drug at UAB

(N=512), patients living in neighborhoods of high vs. low disadvantage had similar odds of cancer clinical trial eligibility, interest, and invitation, yet 3.4 times higher odds of declining enrollment, potentially due to financial barriers.¹⁶

3. Study Objectives

2.1 Overall objective and hypothesis: Our overall objective is to *innovatively use a dose-finding approach* to identify the recommended reimbursement amount for women with breast cancer enrolled in a clinical trial. We *hypothesize* that optimal reimbursement for trial-related expenses will decrease patient financial toxicity and increase trial retention. The *rationale* is that understanding the impact of reimbursement for trial-related costs will aid in addressing socioeconomic barriers to trial participation, thus allowing for more diversity in trial enrollment and ensuring equitable efficacy of cancer treatments when used in real-world clinical settings.

2.2 Specific aims: To accomplish this overall objective, we will propose the following specific aims:

Aim 1. Identify the recommended reimbursement amount in trial-enrolled women with breast cancer experiencing financial toxicity. We propose a pilot reimbursement dose de-escalation trial (continual reassessment method design; N=30) testing a monthly reimbursement for trial-enrolled patients who screen positive for financial toxicity. We will oversample patients who are Black (50%) or residing in rural locations (50%). Monthly patient-reported financial toxicity and reimbursement acceptability and appropriateness will be captured. Reimbursement dose will start at \$1000 and de-escalate if patients find the reimbursement dose suitable (negative financial toxicity screen, reimbursement dose deemed acceptable/appropriate).

Aim 2. Explore patient perceptions of trial reimbursement amounts. Using semi-structured interviews, we will explore the effects of reimbursement on (1) specific covered and uncovered trial-related costs, (2) financial toxicity, and (3) current retention and future participation in clinical trials.

4. Investigation Plan and Study Procedures

4.1 Study design and population: This will be a prospective, health services research study modeled after a traditional, dose de-escalation phase I trial design. The study population will include women with early stage breast cancer currently enrolled in the Investigation of Serial studies to Predict Your Therapeutic Response with Imaging and Molecular AnaLysis (I-SPY TRIAL 2) or metastatic breast cancer enrolled in any clinical trial at the UAB Medical Oncology Clinic.

4.2 Study duration: Two years.

4.3 Participants and recruitment:

4.3.1 Inclusion criteria: Participants will be women with early stage breast cancer currently enrolled in the Investigation of Serial studies to Predict Your Therapeutic Response with Imaging and Molecular AnaLysis (I-SPY TRIAL 2) or metastatic breast cancer enrolled in any clinical trial at the UAB Medical Oncology Clinic.

- 4.3.2 Exclusion criteria: Reasons for study exclusion include non-English speakers.
- 4.3.3 Sampling: Using standard-of-care patient-reported data collected in clinic, eligible patients will have screened positive for financial toxicity using the validated Comprehensive Score for financial Toxicity¹⁴ (COST; scored 0-44, scores < 26 indicate financial toxicity). Eligible patients will be approached during their clinic visit.
- 4.3.4 Informed consent: Informed consent will be obtained by a study coordinator through an informed consent form if the patient is interested.
- 4.4 Approach:
- 4.4.1 Aim 1: We will use the continual reassessment method phase I dose de-escalation clinical trial design under the assumption that financial toxicity may increase when the reimbursement “dose” decreases. Continual reassessment method is a model-based trial design that informs how the reimbursement “dosage” should be adapted for the next patient cohort based on past trial data.^{17, 18} The parameters to be used in the continual reassessment method are listed below.
- 4.4.1.1 Number of doses: We suspect six reimbursement dose amounts will be assessed. However, the number of dose amounts may decrease if a cohort finds their reimbursement dose amount as unsuitable (at least 1 of the 3 de-escalation criteria are not met in 2 patients), in which no dose de-escalation will occur in the next cohort.
- 4.4.1.2 Target toxicity level: The “toxicity” amount will be set at 40% (de-escalation criteria unmet in 2/5 patients) due to the low-risk nature of the “dose,” which is money rather than drug. Note that toxicity in this study is defined as suitability of the reimbursement dollar dose defined by 3 patient-reported measures: (1) financial toxicity (defined as out-of-pocket costs and accompanying psychological distress), (2) acceptability of the reimbursement dose, and (3) appropriateness of the reimbursement dose.
- 4.4.1.3 Dose-toxicity model: We will use a one-parameter logistic model.

Table 1. Dose toxicity skeleton.

[figure not shown]
Dose number	Reimbursement dose amount	Decrease from starting dose in \$100 units	Prior probability of dose-limiting toxicity
1	\$1000	0.001	0.05
2	\$900	1	0.1
3	\$800	2	0.2
4	\$700	3	0.3
5	\$600	4	0.45
6	\$500	5	0.6

- 4.4.1.4 Dose-toxicity skeleton: Shown in **Table 1**.

As this is a dose de-escalation trial testing the feasibility of a dollar decrease in reimbursement from a maximum of \$1000, we are assessing the minimally tolerated dose. This refers to minimum dollar amount needed to alleviate trial-related financial toxicity for patients participating in I-SPY TRIAL2. With the data fitted to a logistic model, the minimally tolerated dose should be around

[figure not shown]
\$630 (i.e., a decrease of about \$370 from the starting dose of \$1000), and we would expect to detect it at the 5th dose (**Figure 1**).

Figure 1. Number and spacing of doses.

The operating characteristics also appear fine using a one-parameter logistic model (**Figure 2**).

Figure 2. Dose-toxicity scenarios.

4.4.1.5 Method of inference: We will use a Bayesian approach with informative priors.

4.4.1.6 Decision rules: We will choose the reimbursement dose with an estimated probability of a minimally acceptable, appropriate, and financial toxicity-limiting reimbursement dose closest to, but not greater than, the optimal reimbursement level.

4.4.1.7 Sample size and cohort size: Our total sample size for women with early stage breast cancer patients is 30, comprised of 6 cohorts of 5 patients

each. Our total sample size for women with metastatic breast cancer patients is also 30, comprised of 6 cohorts of 5 patients each.

4.4.1.8 Safety modifications: We expect minimal safety concerns with this study, since there is no medical/drug intervention.

4.4.1.9 Stopping rules: Early termination of phase I trials often occurs if adding additional patients to the trial will not result in changes to the identified optimal dose. As this is not a true phase I trial, but rather a health services pilot feasibility trial anchored within a phase I trial methodological design, no stopping will occur. Enrollment of our targeted 30 patients is necessary to understand our primary feasibility outcomes move our science forward to test outcomes in a larger randomized controlled trial.

[figure not shown]
4.4.1.10 Patients will be dosed in cohorts of 5, with a maximum available sample size of 30 early stage and 30 metastatic breast cancer patients. The first cohort of 5 patients will be enrolled at the first reimbursement dose level of \$1000 per month for 4 months (\$4000 per patient in total). Patients will be surveyed biweekly to determine patient financial toxicity (COST tool¹⁹), acceptability of the reimbursement dose (Acceptability of Intervention Measure²⁰), and appropriateness of the reimbursement dose (Intervention Appropriateness Measure²⁰). Participants will be surveyed in-person at baseline, then biweekly over the phone. Semi-structured interviews will be completed in-person, with an option for completion virtually if the participant prefers. At the end of the 4-month period, reimbursement dose suitability will be determined as suitable by a cumulative negative financial toxicity screen and reimbursement dose deemed acceptable and appropriate in at least 4 patients (**Table 2**). If the reimbursement dose is found suitable (all of the 3 criteria are met in at least 4 patients), we will de-escalate the reimbursement dose for the next cohort of 5 patients (**Figure 3**). If the reimbursement dose is found unsuitable (at least 1 of the 3 criteria are not met in 2 patients), the next cohort of 5 patients will be enrolled at the same reimbursement amount (\$1000 per

Table 2. Reimbursement dose suitability and de-escalation criteria.

Reimbursement Dose Suitability Criteria	Instrument	Scoring	De-Escalation Criteria
Negative financial toxicity screen	Comprehensive Score for financial Toxicity (COST) ¹⁹	Scored 0-44, scores < 26 indicate financial toxicity	Average score ≥ 26
Reimbursement dose acceptable	Acceptability of Intervention Measure (AIM) ²⁰	4-item, 5-point Likert scale; higher scores indicate greater acceptability	Average score ≥ 4
Reimbursement dose appropriate	Intervention Appropriateness Measure (IAM) ²⁰	4-item, 5-point Likert scale; higher scores indicate greater appropriateness	Average score ≥ 4

month for 4 months). This sequence will continue until 30 patients have received the reimbursement intervention.

Figure 3. Study schema.

4.4.1.11 Justification of starting dose: The initial \$1,000 dose is based on a prior estimate of a logit model with $\beta_0 = -2.79$ and a slope $\beta_1 = 0.64$ for the dose in \$100 units. This was based on consensus among the investigators in the study and data from three studies:

4.4.1.11.1 In a study of 213 patients with cancer enrolled in a phase I trial at MD Anderson, Huey and colleagues found 48% of patients had out-of-pocket costs of at least \$1,000 per month.²

4.4.1.11.2 In a study of 153 patients with cancer enrolled on a clinical trial and receiving financial assistance through a cancer care equity program at Massachusetts General Hospital, reimbursements averaged \$185 per month for patients living in Massachusetts, \$300 per month for patients living in New England, and \$900 per month for patients living outside of New England.³

4.4.1.11.3 In a study of 66 patients with cancer enrolled on a clinical trial and receiving financial assistance through a financial reimbursement program at UCSF and USC, 11% of patients reported incurring out-of-pocket costs of at least \$1,000 per month.⁴

Notably, we suspect women with breast cancer receiving care at UAB may have higher out-of-pocket costs associated with clinical trial participation than what was found in these studies due to high poverty rates, uninsurance, long travel distances, and lost productivity. Thus, based on the three studies completed in other US regions, as well as the unique cost-related barriers to trial participation in Alabama-based patients, we do not believe \$1,000 per month to be an excessive starting point. As this is a pilot study, there is a chance that the patients will find the \$1,000 per month unsuitable. Reasons why the patients find this amount unsuitable will be explored in our qualitative interviews. Due to budgetary constraints of the funding mechanism, we are unable to offer more than \$1,000 per month. However, both the quantitative and qualitative data regarding suitability will inform our next study testing reimbursement in a larger sample.

4.4.2 Aim 2: Qualitative, semi-structured interviews will be conducted with patients from Aim 1. Interview questions will explore the effects of reimbursement on (1) specific covered and uncovered trial-related costs, (2) financial toxicity, and (3) current retention and future participation in clinical trials. Interviews will be audio-recorded and transcribed for analysis.

5. Data Analysis

5.1 Aim 1

- 5.1.1 Sample size: A total of 30 women with early stage breast cancer and 30 women with metastatic breast cancer will be recruited for our study. We will oversample patients who are Black (50%) or residing in rural locations (50%) to ensure representation from patient groups routinely underrepresented in clinical trials. As this is a pilot data funding mechanism, it was necessary to balance both sample size and budgetary constraints. After accounting for research staff (research assistant, biostatistician) and study expenses (interview transcription, publication fees), cohort sizes of 5 were the maximum potential size assuming the potential of no de-escalation of the \$1,000 per month reimbursement constrained within a 2-year timeframe.
- 5.1.2 Power: Because this is a pilot study to assess feasibility of trial-related cost reimbursement to be used in a larger phase II trial, no true power calculation is required.²¹ Feasibility benchmarks will be defined as 80% retention of patients and retained patients completing at least 75% of bi-weekly surveys while enrolled.
- 5.1.3 Analysis: Descriptive sociodemographic, survey, and feasibility data will be calculated for all patients. Comparisons by race (white/black) and residence (rural/urban) will be investigated. Mean differences, or effect sizes, will be calculated using Cohen's d or Cramer's V to determine the magnitude of relationships in bivariate associations.²²

5.2 Aim 2 Analysis: Using a directed content analysis approach,²³ a codebook will be created as guidance. The initial codebook will be reviewed by [name] (*collaborator*, medical oncologist) and [name] (*collaborator*, health economist). Thematic analysis will be conducted by [name] (*PI*) and [name] (*research assistant*, disparities researcher) and used to qualitatively code interview text into codebook categories. Thematic concordance between [name] and [name] will be reviewed after every 2-3 interviews. If needed, new codes or subcodes will be created based on the data. Newly added codes will be used to create a final codebook. All interview transcripts will be reviewed using the final codebook. Themes by race and residence will be investigated.

5.3 Secondary data analysis: To further understand potential cost and travel burdens to participate in a cancer clinical trial, we will abstract trial and patient data from UAB oncologic therapeutic trial treatment protocols and the OnCore database. Abstracted trial data will include factors associated with financial burden, such as visit frequency and sponsor payment to participants. Abstracted patient data will include sociodemographic and clinical characteristics, such as home address (to map distance/time required to travel to clinic).

6. Data and Safety Monitoring

- 6.1 Safety monitoring: [name] will be responsible for reviewing and monitoring all study data and any adverse events during data collection. The investigative team will meet with study personnel every 2 weeks to evaluate study progress, including

periodic assessments of data quality and timeliness, participant recruitment, participant risk versus benefit, and other factors that can affect study outcomes. Any unanticipated problems and adverse events will be reported to the UAB IRB according to policies. The risks involved for study participation are minimal and do not put safety at risk.

6.2 Data: Survey responses will be kept within an encrypted, password-protected database and stored in network drives with restricted access on a password protected computer. Data from this study housed at UAB will be destroyed within three years of study completion.

7. **Benefits**

The potential benefits include increased understanding of (1) the optimal reimbursement “dose” to reduce trial-related financial toxicity, (2) specific categories of trial-related expenses that could result in barriers to participation if not reimbursed, and (3) the impact of reimbursement on trial recruitment and retention outcomes. This understanding could benefit patients by reducing the trial-related financial toxicity in women with breast cancer, dismantling trial access barriers, and promoting greater diversity in trial samples.

8. **Potential Risks and Solutions**

- Concern: Reimbursement could be considered as undue influence for research participation.
- Solution: Reimbursement for trial-related expenses is considered a “just and fair,” non-coercive practice against patient exploitation by both the US Food and Drug Administration and American Society for Clinical Oncology.²⁴⁻²⁶ Coercion to participate in research is unlikely in our study since eligible women will have already enrolled in the I-SPY TRIAL 2.
- Concern: The US Department of Health and Human Services Office of Human Research Protections advises that ethical payments to research participants should not be “excessive.”²⁷
- Solution: Our calculations assume the highest reimbursement dose is not excessive, but rather allows for participants to reach the break-even point, compensating for incurred trial-related out-of-pocket costs. I-SPY TRIAL 2 participants have weekly infusion treatments for the first 12 weeks of enrollment, followed by 4 cycles of standard chemotherapy every 2-3 weeks, resulting in 16 infusion visits alone. Based on the initial reimbursement dose of \$4000 over 4 months, the estimated reimbursement per infusion visit is \$250. This would ideally reimburse any medical expenses uncovered by insurance, transportation to and from clinic, parking, food, lodging, caregiver expenses, and lost wages from time off work. Notably, participants also have trial-required scans, labs, biopsies, and surgery, further increasing trial-related costs. Thus, we believe the estimated maximum reimbursement is potentially less than the break-even point.
- Concern: Patients included in this reimbursement dose de-escalation trial will have already been enrolled or enrolling onto a clinical trial, thus biasing the sample towards patients who do not have cost-related barriers to trial participation or who are willing to accept the complete cost of trial participation.
- Solution: Risk of financial toxicity is not fixed and may increase with increasing time on trial. Identifying the optimal reimbursement “dose” may therefore increase likelihood of

not only trial recruitment for individuals with financial barriers, but also trial retention for individuals experiencing trial-related financial toxicity. It is also unclear if patients are informed of or fully understand trial-related costs during trial enrollment. These recruitment and retention outcomes will be explored in our qualitative interviews (Aim 2).

- Concern: Enrollment onto I-SPY TRIAL 2 is too low to accrue patients to this reimbursement dose de-escalation trial.
- Solution: We will expand to other UAB breast cancer clinical trials if necessary.

9. Confidentiality

Breach of confidentiality will be minimized by removal of HIPPA-protected information from the dataset, use of secure data transfer, and encrypted data storage on a password-protected computer.

10. References

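### The stated two years equals six 4-month cohorts run end to end, leaving no time for accrual, close-out interviews or analysis

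*Combined protocol and SAP*

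**What the plan says.** Section 4.2 of the combined protocol and SAP reads "Study duration: Two years". Section 5.1.1 uses the same limit to justify the cohort size: five was the largest affordable number, "constrained within a 2-year timeframe".

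Section 4.4.1.7 sets the early-stage sample, which "is 30, comprised of 6 cohorts of 5 patients" each, and adds: "Our total sample size for women with metastatic breast cancer patients is also 30, comprised of 6 cohorts of 5 patients each".

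Section 4.4.1.10 fixes the order of events. "At the end of the 4-month period, reimbursement dose suitability will be determined". If at least 4 of the 5 patients meet all three criteria, "we will de-escalate the reimbursement dose for the next cohort of 5 patients"; if not, the next five receive the same amount. The sequence goes on until 30 patients have been treated. Section 4.4.1.9 says there will be no stopping and that the 30 patients are needed.

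Section 4.4.1.4 puts the expected answer near $630 and expects to find it at the 5th dose, which Table 1 lists as $600.

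The documents give no accrual rate, enrolment window or overlap between cohorts. They do not say whether the two disease groups run in parallel.

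**The concern.** The next cohort's amount is unknown until the current cohort has finished its 4 months, so the cohorts cannot overlap under the written rule. Six of them fill 24 months exactly. That holds only if all five patients in a cohort start together and the next five start as soon as the previous cohort is judged. Nothing is left for enrolling patients, for interviews after the last payments, or for analysis.

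The design starts at $1000 and moves down at most one step per cohort, so the lower amounts are reached only by the last cohorts. If two years is a firm limit, any lost time falls on the cohorts that can reach the dose where the plan expects its answer. If it is not firm, the duration in 4.2 is wrong, and so is the time basis on which 5.1.1 rests the cohort size.

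**Working it through.** **Inputs.** Duration 24 months (4.2, 5.1.1); six cohorts of five per disease group (4.4.1.7); 4 months before each decision (4.4.1.10); prior probabilities of unsuitability 0.05, 0.10, 0.20, 0.30, 0.45, 0.60 for doses 1 to 6 (Table 1); prior logit intercept -2.79 and slope 0.64 per $100 (4.4.1.11); target 40% (4.4.1.2).

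**The plan's own figures.** 6 x 4 = 24 months, the stated two years. The target decrease is (logit(0.40) + 2.79)/0.64 = (-0.405 + 2.79)/0.64 = 3.73 units, or about $627, which agrees with the stated $630.

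**Adding accrual.** Let m be the months from the decision on one cohort to the start of the last patient in the next, after any screening ahead. The documents give no value, so m is an assumption shown as a range. With the disease groups in parallel, cohort k ends at k(4+m) months.

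| m (months) | Cohort 5 ends | Cohort 6 ends | Cohorts complete by month 24 |
|---|---|---|---|
| 0 | 20 | 24 | 6 |
| 0.5 | 22.5 | 27 | 5 |
| 0.8 | 24 | 28.8 | 5 |
| 1 | 25 | 30 | 4 |
| 2 | 30 | 36 | 4 |

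Cohort 6 finishes by month 24 only if m = 24/6 - 4 = 0. Cohort 5 finishes by then if m is at most 24/5 - 4 = 0.8. Without screening ahead, that means 5/0.8 = 6.25 patients a month in each disease group. At m = 1, 4 x 5 = 20 of the 30 patients per group are complete at month 24, and the lowest amount with complete data is at best $700, the 4th dose.

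**What the sixth cohort is worth.** Take the Table 1 priors as true and apply the written rule: step down if at most 1 of 5 is unsuitable, otherwise stay. The binomial chance of stepping down from doses 1 to 4 is 0.977, 0.919, 0.737 and 0.528.

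- Reaching the 5th dose at cohort 5 needs four steps in a row: 0.977 x 0.919 x 0.737 x 0.528 = 0.35.
- The chance that cohort 4 is at dose 4 is 0.662, and at dose 3 it is 0.329. The chance that cohort 5 is at dose 4 is therefore 0.662 x (1 - 0.528) + 0.329 x 0.737 = 0.555.
- By cohort 6 the 5th dose has been reached with chance 0.350 + 0.555 x 0.528 = 0.643.

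These figures follow the written 4-of-5 rule. They are not a simulation of the continual reassessment method.

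**The case against.** The best defence is that m could be small. Patients are already in a trial, they are identified from COST data collected in routine care (4.3.3), and metastatic patients may come from any trial at the clinic. Candidates could be found while the previous cohort is followed. Section 8 answers the worry about low I-SPY 2 enrolment by allowing other breast cancer trials at the centre. This stands as a reason why m may be low, and at m = 0 six cohorts just fit. But the plan describes no such queue and no common start. Waiting also has a price in I-SPY 2: section 8 gives 12 weekly infusions and then 4 cycles every 2 to 3 weeks, so 12 + 8 = 20 to 12 + 12 = 24 weeks in all. A wait of up to 4 months would use most of the visits that the payment is meant to cover.

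Some stronger readings are not supported:

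- A reader might infer that two years cannot reach the 5th dose. It can: that dose needs only five cohorts, which fit for m up to 0.8.
- A reader might infer that the study will be cut off at month 24. Sections 4.4.1.9 and 4.4.1.10 point instead to an overrun, since the sequence continues until 30 patients are treated and there is no stopping. Section 4.4.1.1 also accepts that fewer than six amounts may be tested.
- A reader might infer one shared sequence of twelve cohorts. Section 4.4.1.7 gives each disease group its own six.
- A reader might treat the 50% Black and 50% rural figures as quotas that slow accrual. The plan calls this oversampling and gives no case mix from which to judge the effect.

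It is also fair to say that this is a feasibility pilot, that its benchmarks (80% retention, 75% survey completion) are not tied to calendar time, and that a longer study biases no estimate.

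**Conclusion.** The point holds as an inconsistency of duration. Two years, six strictly sequential 4-month cohorts and no stopping are compatible only with zero unabsorbed accrual time and nothing after the last cohort. The overrun on six cohorts is 6m months: 3 at m = 0.5, 6 at m = 1, 12 at m = 2, plus analysis time. The result rests on the two disease groups running in parallel and on m, which the documents do not give.

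The effect on the study's answer is conditional. If the study runs until 30 patients per group are treated, only the stated duration is wrong. If it ends at two years, any positive m up to 0.8 costs the sixth cohort and lowers the chance of having tested the 5th dose from about 64% to 35%. Above 0.8, the fifth cohort is incomplete as well.

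**What to change.** Restate the duration in 4.2 and 5.1.1 as 6(4+m) months plus time for analysis. Give the accrual assumption behind m, including any screening ahead, and state that the two disease groups run in parallel.

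If two years is a hard limit, state instead how many cohorts and patients per group will be complete by then and the lowest amount that can be tested, and bring 4.4.1.7, 4.4.1.9 and 4.4.1.10 into line.

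The cost is a change of wording and either a longer stated duration or a smaller stated size. Because 5.1.1 ties the cohort size to two years, a longer study also means checking the budget, for which the documents give no figures.

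A time-to-event continual reassessment method, which would let cohorts overlap, is not needed to resolve this. Suitability is a cumulative average score (4.4.1.10, Table 2) that can cross its threshold in either direction, so that route would mean redefining the endpoint and the decision rule.

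### Entry and the COST criterion share one cut-off and the study baseline has no stated role, so regression to the mean may bias the recommended amount downward

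*Combined protocol and SAP*

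**What the plan says.** Entry (4.3.3 Sampling) is decided "Using standard-of-care patient-reported data collected in clinic": "eligible patients will have screened positive for financial toxicity using the validated" COST. The instrument is "scored 0-44, scores < 26 indicate financial toxicity". No repeat or confirmatory screen is described.

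The COST de-escalation criterion in Table 2 is "Average score ≥ 26": the same instrument and the same cut-off. Table 2 adds AIM and IAM averages of at least 4. Section 4.4.1.10 lowers the amount for the next cohort when "all of the 3 criteria are met in at least 4 patients", out of a cohort of 5.

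On timing, 4.4.1.10 states: "Participants will be surveyed in-person at baseline, then biweekly over the phone". The baseline is therefore collected, but no rule uses it to confirm entry, to adjust or to measure change. The text does not say whether it enters the average.

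Section 2.1 hypothesises that optimal reimbursement "will decrease patient financial toxicity and increase trial retention". Section 5.1.3 plans descriptive data, comparisons by race and residence, and bivariate effect sizes. It has no within-patient change in COST. All patients are reimbursed.

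**The concern.** Patients are selected because a noisy score fell below a line, and are then judged on whether a later average of the same score lies above that line. Some were near or above 26 in truth and scored low at the clinic. Their later average will tend to be 26 or more whatever they are paid. Without an unpaid group or a use of the baseline, nothing in the plan separates these patients from those whom the payment helped.

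The design's product is the smallest amount that relieves trial-related financial toxicity (4.4.1.4). If some COST passes owe nothing to the payment, observed unsuitability at each amount is diluted. Both the 4-of-5 rule and the fitted curve then lean towards lower amounts. That amount is meant to inform the next, larger study.

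**Working it through.** **The plan's own figure.** Section 4.4.1.11 gives β0 = -2.79 and β1 = 0.64 per $100 decrease; 4.4.1.2 sets the target at 0.40. Then x = (logit 0.40 - β0)/β1 = (-0.405 + 2.79)/0.64 = 3.726, so the amount is 1000 - 373 = $627. The plan says about $630, so its figure reproduces.

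**COST with no payment effect.** Take score = true level + independent error, total variance 1, with reliability r the true share. The cut-off c is the normal quantile of the share below 26. The mean of k later scores has variance r + (1-r)/k and correlation r/√(r + (1-r)/k) with the screen. I take k = 8, my count from "Patients will be surveyed biweekly to determine patient financial toxicity" over 4 months. Only the share below 26 and r matter. The plan gives neither for this population, so both are assumed. The nearest local figure is 29% with financial distress among 1,564 oncology patients (Preliminary Studies), instrument not stated.

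Hand check at a 50% share, where the probability is 1/2 - arcsin(correlation)/π. With r = 0.7, the correlation is 0.7/√0.7375 = 0.815, arcsin is 0.953, and 0.5 - 0.303 = 0.197. The simulation (2 million draws) gives 0.196.

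| Share below 26 | r | Later mean ≥ 26, no payment effect | Same, if baseline also < 26 | Baseline ≥ 26 | Amount at which observed unsuitability reaches 40% |
|---|---|---|---|---|---|
| 29% | 0.6 | 41% | 23% | 43% | $500 |
| 29% | 0.7 | 34% | 17% | 37% | $550 |
| 29% | 0.8 | 26% | 12% | 30% | $585 |
| 29% | 0.9 | 18% | 7% | 21% | $615 |
| 50% | 0.6 | 23% | 12% | 30% | $600 |
| 50% | 0.7 | 20% | 9% | 25% | $610 |
| 50% | 0.8 | 16% | 7% | 20% | $620 |
| 50% | 0.9 | 11% | 4% | 14% | $625 |
| 70% | 0.6 | 11% | 6% | 18% | $635 |
| 70% | 0.7 | 10% | 5% | 16% | $635 |
| 70% | 0.8 | 8% | 4% | 13% | $630 |
| 70% | 0.9 | 6% | 2% | 9% | $630 |

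Columns 3 to 5 are shares of screen-positive patients (column 4: of those confirmed at baseline).

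**Effect on the amount (last column).** The payment effect was set so that patients whose true score is below 26 follow the plan's prior curve. AIM and IAM were taken as always met, with no time trend, on a $5 grid. Against $627, the downward shift is $12-127 at a 29% share, $2-27 at 50%, and none at 70%. With r of 0.7 or more the largest shift is 627 - 550 = $77.

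**A cruder check.** If a fraction q of would-be failures pass anyway, observed unsuitability is (1-q)p, and 40% is reached at p = 0.40/(1-q). For q = 0.2, p = 0.50, x = 2.79/0.64 = 4.36 and the amount is $564. For q = 0.1 it is $599 and for q = 0.3 it is $519. Under the plain 4-of-5 rule over six cohorts, the mean amount assigned to the sixth cohort falls from $625 to $612, $598 and $583 for q = 0.1, 0.2 and 0.3.

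**Limits.**
- With no payment effect, at least 4 of 5 patients meet the COST criterion with probability 9.5% at worst (q = 0.41), and at most 1.2% when 50% or more score below 26.
- Including the baseline in the average hardly matters (41.0% against 40.9%).
- Aim 1 in section 2.2 speaks of monthly capture and 4.4.1.10 of biweekly surveys. These must be reconciled, but with k = 4 the 20% cell becomes 0.5 - arcsin(0.795)/π = 21%.
- Restricting to baseline below 26 cuts the artefact by roughly 45-60%. In the same model the 40% point then lies at $650-680, above $627, because patients selected twice are more severely affected.

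**The case against.** A reader might infer that a patient already at 26 or more at baseline is suitable at every amount and counts as a reimbursement success. Table 2 does not support this: AIM and IAM must also average at least 4, and patients are not selected on either. Someone averaging 30 on COST who finds the amount unacceptable counts as unsuitable. The dollar shifts above are therefore towards the upper end, because they take AIM and IAM as always met. What remains is the direction: failing any one criterion makes a patient unsuitable, so spurious COST passes cannot raise observed unsuitability.

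A reader might also infer that the recommended amount will be too low. That goes too far. Section 8 says that financial toxicity may rise with time on trial, which would work the other way. Section 4.4.1.11 expects higher costs here than in the cited studies, so a large affected share, where the shift vanishes, is plausible.

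That the entry score is a single measurement is the natural reading of 4.3.3 but is not stated. The absence of a control is a stated choice for a pilot that leads to a larger randomised trial, and I do not ask for one. Neither point explains why a baseline that is collected goes unused.

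**Conclusion.** The concern holds as a likely, unquantified bias and as a gap in the analysis. About 6-34% of screen-positives would meet the COST criterion with no payment effect, assuming 29-70% of patients below 26, reliability 0.7-0.9, eight later surveys, independent errors and no time trend. At reliability 0.6 the top figure is 41%. The effect on the recommended amount runs from no downward shift to about $125. The upper end needs both the 29% share and reliability 0.6. The documents fix none of these inputs, so they support "may bias downward" and no firmer statement. Separately, the hypothesis that financial toxicity decreases has no analysis that tests or estimates a decrease.

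**What to change.** In 5.1.3:
- Add the within-patient change from the in-person baseline COST to the mean COST after first payment, overall and by amount, with 95% CI. Use the baseline and not the screening score: patients are selected on the latter, so a change from it would contain the regression. Note that survey mode changes from in-person to phone, and that intervals by amount will be wide with cohorts of 5.
- Report how many patients have a baseline COST of 26 or more.
- Re-estimate the dose-toxicity curve, as a sensitivity analysis, in patients whose baseline COST is below 26. State that this roughly halves the artefact and does not remove it. As it also selects more severely affected patients, read it beside the main estimate and not as a corrected value.

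In Table 2, state that the COST average uses only surveys after the first payment. This is a clarification with little numerical effect.

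These changes cost wording and analysis time; the data are already collected. The change score remains uncontrolled, so a time trend stays mixed with the payment effect.

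Requiring COST below 26 at baseline before first payment is optional. At reliability 0.7-0.9, about 9-37% of screen-positives would not confirm, or roughly 3 to 11 of every 30, and section 8 already lists low I-SPY accrual as a concern. Applied after enrolment, it would leave cohorts of fewer than 5, and the 4-of-5 rule would have to be rewritten.
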